4.10 MILESTONES

The start of data collection was in February 2013 in Sweden, May 2013 in the UK, and September 2014 in Spain. The end of data collection was to be based on the linaclotide uptake and has been extended to

December 2018 in Sweden and Spain, and the most recent HES and CPRD data available by the time of data extraction in 2024 in the UK.

Due to delays on data processing from the Swedish data custodians, data became available for the planned analyses in December 2019. The validation questionnaires to GPs in the UK were eventually available electronically in February 2020. Very low response rate of GPs to questionnaires to validate SCD diagnosis, because of COVID-19 shut down in the UK, motivated a proposal that the validation questionnaires to the GPs in the UK would be sent out again in Q1 2021, aiming to improve the response rate. Continued COVID-19 related shut down in the UK necessitated further postponement of sending the validation questionnaires to GPs in the UK to Q4 2021. When approached on this matter in Q4 2021, the planning manager at CPRD explained that CPRD paused GP questionnaire studies until further notice due to the shortage of primary care clinical staff in the UK to continue focusing their resources on supporting COVID-19 activities. In Q2 2022, CPRD confirmed that they have reopened GP questionnaire services and suggested the study team to resume the validation questionnaires in Q4 2022 given CPRD's resources and current pipeline of work. In the protocol version 12.0, the MAH proposed to reopen the UK validation study in October 2022 until January 2023 with planned study report date in Q3 2023. In response to the MAH's proposal, in the preliminary assessment report for the PASS protocol amendment submission (3rd Oct 2022), PRAC requested the MAH to extend the UK observational period up to the most recent possible date in order to include all available data and to revise the data collection period in the milestones accordingly, without further postponement of the final report (Q3 2023). The MAH contacted CPRD to confirm next steps for data extraction and validation study rerun. CPRD required that the MAH submit a new protocol to the CPRD review committee before requesting the new datasets and re-running the validation study. This is due to the change of dataset from CRRD GOLD to CPRD GOLD and CPRD Aurum, and the change of the observational period. Of note, most practices have moved from CPRD GOLD to CPRD Aurum in the last few years, which makes the CPRD GOLD dataset much smaller. In parallel the MAH informed the EMA / PRAC Rapporteur on 31st March 2023, of the challenges faced due to the protocol update and the consequential impact to the final PASS CSR deliverable. The process from the submission of the protocol amendment until receiving datasets from CRPD is approximately 3-4 months. The MAH submitted a new protocol to CPRD in April 2023 and expected to receive approval and the new datasets in Q3 2023. The MAH proposed to identify the new SCD cases and controls from the new datasets first and reopen the UK validation study in Q4 2023 - Q1 2024 to validate the new cases and controls. However, due to delays in data access, the MAH received the latest CPRD GOLD and CPRD Aurum data cut in March 2024. The validation will be conducted in Q2-Q3 2024.

Study reports will be issued when Periodic Safety Update Reports (PSURs) are due (every six months for the first two years and yearly thereafter). No additional interim report is planned for this study, and the final report of study results will be submitted to PRAC in Q1 2025.

5 AMENDMENTS AND UPDATES

Version	Date	Section of study protocol	Amendment or update	Reason
5.0	17 Jul 2015	N/A	Protocol version approved by PRAC.	N/A
6.0	07 Jun 2016	Marketing Authorisation Holder Annex 3: Physician's Questionnaire	Change from Almirall to Allergan. Change to the proposed questionnaire.	Change in MAH responsible for linaclotide. Improve questionnaire comprehension.

6.1	26 Jan 2017	Several sections in protocol abstract and main text	Timeline extended by one year and agreed with Rapporteur	2016 progress report counts of linacotide users lower than planned
6.2	08 Jan 2018	Annex 3: Physician's Questionnaire	Language added to introduction paragraph	To ensure physicians only provide information about requested patient
7.0	18 Feb 2019	Several sections in protocol abstract and main text	Timeline extended by six months; change in Spain, from case validation through questionnaires to GP to free-text review of medical records; text added for clarity	The overall timelines are extended due to ongoing delays in data receipt from the Swedish authorities. The Spanish data custodian no longer offers the possibility to conduct validation using questionnaires to GP.
8.0	05 November 2020	Milestone Table	Timeline extended by one year	Very low response rate from UK GP to the questionnaire to validate SCD diagnosis, in February 2020, possibly because of the shutdown in the UK due to COVID 19 infections. Questionnaire will be resent in Q1 2021
9.0	01 March 2021	Milestone Table	Timeline extended by one year	Continued COVID-19 related shut down in the UK necessitated further postponement of sending the validation questionnaires to GPs in the UK to Q4 2021
10.0	07 March 2022	Responsible Parties; Milestone Table; Nested Case Control Analyses	Updated MAH contact details; updated milestone timelines; added proposed sensitivity analyses	CPRD paused GP questionnaire studies until further notice, due to the need for primary care clinical staff in the UK to continue focusing their resources on supporting clinical services; sensitivity

				analyses are proposed to deal with algorithm-classified cases and controls that are unable to be validated.
11.0*	04 August 2022	Milestone Table Marketing Authorisation Holder	Updated milestones Change of MAH from Allergan to AbbVie	MAH proposes to reopen UK validation study in October 2022 until January 2023 with planned study report date in Q3 2023 Update to the MAH from "Allergan Pharmaceuticals International Ltd" to "AbbVie Deutschland GmbH & Co. KG"
12.0	09 November 2022	Data sources Milestones Time periods and dates	Update data sources in the UK to CPRD GOLD and Aurum. Update the last data collection to March 2021 or the most recent HES data available. Update milestones to consider the time to obtain protocol amendment approval from CPRD, data extraction, analyses of new data, re-run of validation study.	Requested by the Health Authority
13.0	01 August 2023	Data sources Milestones Time periods and dates	Update data sources in the UK to CPRD GOLD and Aurum. Update the last data collection to the date of the most recent HES and CPRD data available in 2023 at the time of data access. Update milestones to consider the time to obtain protocol application approval	Update to obtain the most recent data was requested by the PRAC Due to the extension of the data collection and challenges faced by Evidera/MAH with CPRD, this resulted in a request to extend the final PASS CSR date by the MAH.

			from CPRD, data extraction, analyses of new data, re-run of validation study.	
13.1	12 October 2023	Rationale & Background Data Sources Research Method Limitations	Include background information on presentation of severe complications of diarrhoea. Update to representativeness of CPRD GOLD and CPRD Aurum databases. Update control selection criteria for CPRD GOLD and Aurum. Add different coverage period for HES linkage	Requested by CPRD Requested by the PRAC Requested CPRD Requested by CPRD
13.2	15 July 2024	Milestones Updates across sections	Update to reflect the progress of CPRD data access and the UK validation study Updates across multiple sections based on latest available data and information	Updated milestone information provided for extension request via type II variation process
13.3	15 October 2024	Study size Cohort size	Update to include additional text on cohort sample sizes to detect certain ORs. Update to remove some other text	Requested by PRAC Text previously included, now deemed unnecessary.

* Changes requested, pending acknowledgement by PRAC. In this version 13.2, the timelines for the study milestones have been updated to reflect the plan of re open UK validation study in Q2 2024. The updated timelines are provided in [Table 1](#) in the Milestones section below.

6 MILESTONES

Table 1. Milestones

Milestone	Date
Start of data collection	February 2013 (Sweden) May 2013 (UK) September 2014 (Spain)

End of data collection	Electronic datasets: 
- Spain and Sweden: Data collected up to December 2018. Effective date when data up to December 2018 can be accessed (incorporating time for data access applications to be processed)- UK: the most recent HES and CPRD data available at the time of data access in 2024, i.e., 20 October 2023 for CPRD Aurum, 17 November 2023 for CPRD GOLD 31 March 2021 for HES APC 31 October 2020
------------------------	--

Milestone	Date
	for HES OP, 31 March 2020 for HES AE and 29 March 2021 for ONS death data. Validation: - UK: Q2-Q3 2024 - Spain: Q2 2020 Analytical dataset completely available: Q4 2024
Registration in the EU PAS register	September 2016
Study progress reports	With each PSUR
Interim reports	No
Final report of study results	Q4 2024
EMA submission	Q1 2025

Abbreviations: CPRD Clinical Practice Research Datalink; EU European Union; GP general practitioner; HES Hospital Episode Statistics; PAS post authorisation study; PSUR periodic safety update report; UK United Kingdom; NPR National Patient Register; PDR Prescription Drug Register

7 RATIONALE AND BACKGROUND

IBS is a chronic, relapsing gastrointestinal condition characterised by abdominal pain, bloating, and changes in bowel habits. The first presentation of patients with IBS symptoms to a physician is usually in the 30- to 50-year age group, and there is a decrease in reporting frequency among older subjects (Drossman et al., 2002; IBS Global, 2009). Typically, women are diagnosed with IBS two or three times as often as men in most studies, and all population-based studies have reported a female predominance (Keeling & Fielding, 1975; Thompson, 1984; 1997; Saito et al., 2002). Moreover, women make up 80% of the population with severe IBS (Longstreth & Wolde-Tsadik, 1993). Prevalence estimations vary with the diagnostic criteria used, and in the UK were estimated between 9.5% and 22% (Spiller et al., 2007).

IBS can be classified according to Rome III criteria, on the basis of the stool's characteristics: IBS-D; IBS-C; and IBS-M. Patients can transition among these subgroups (IBS Global, 2009). Approximately one-third of IBS corresponds to IBS-D, one-third to IBS-C, and one-third to IBS-M (Tillisch et al., 2005). When there is insufficient abnormality of stool consistency to meet the criteria for any of the above subgroups, IBS is said to be unsubtyped (Longstreth et al., 2006).

Prior IBS treatments were limited to lifestyle modifications, psychological interventions, and symptomatic treatments (e.g., laxatives, anti-diarrhoeals, and anti-spasmodic agents), or drugs unauthorised for this indication in some of the countries. In a review, current IBS-C treatment options showed limited efficacy, and the risk-benefit profile of early 5-Hydroxytryptamine 4 (5-HT4) agonists restricted clinical use (Fortea et al., 2013).

Linaclotide (Constella®), a guanylate cyclase-C receptor agonist with visceral analgesic and secretory activities, has received approval for its commercialisation. It is the first medicine authorised for the symptomatic treatment of IBS in the EU. The target indication of linaclotide is the treatment of moderate-to-severe IBS-C in adults. Results from clinical trials and real-world research show that most common side effect of linaclotide is diarrhea (Bassotti et al, 2018; Nee et al, 2019). In clinical studies, severe diarrhea associated with dehydration have been reported among 2% of IBS-C patients who were prescribed linaclotide (Rey et al , 2017; Linaclotide Information Sheet, 2023). During post-marketing surveillance, the dehydration might present with tachycardia, hypotension, dizziness, syncope, and electrolyte abnormalities (hypokalemia, hyponatremia), necessitating hospitalization and intravenous fluid therapy (Kalola et al, 2023, Linaclotide information sheet, 2023).

The proposed study will assess the risk of SCD during treatment with linaclotide therapy and other risk factors among patients with IBS-C from three selected European countries: the UK, Sweden and Spain. This study is descriptive and there is not an *a priori* hypothesis.

8 RESEARCH QUESTIONS AND OBJECTIVES

8.1 RESEARCH QUESTIONS

The study will address the following research questions:

- What are the risk factors associated with SCD in patients with IBS-C (specifically linaclotide prescription vs no linaclotide prescription)?
- What is the estimated risk of SCD among IBS-C patients prescribed linaclotide (if allowed by the results of the cases and controls validation as discussed below)?

Both research questions will be assessed in three different countries: the UK, Sweden and Spain

8.2 OPERATIONAL OBJECTIVES

- To estimate the risk (case-control OR) of SCD (case) among patients with IBS-C (source population) who received linaclotide prescription vs those who did not, controlling for other potential SCD risk factors (socio-demographics, comorbidities [up to 15], co-medications [up to 15] and other potential variables of interest [up to 10])
- To describe the crude incidence of diarrhoea among patients with IBS-C (source population)

If allowed by the results of the cases and controls validation as discussed below:

- To describe the crude incidence of SCD among patients with IBS-C (source population) prescribed linaclotide (first-time users)
- To describe the crude incidence of SCD among patients with IBS-C (source population) prescribed linaclotide (first-time users) who are at increased risk of SCD:
 - o Patients ≥ 65 years
 - o Patients with hypertension, diabetes, or cardiovascular disease diagnostic codes

9 RESEARCH METHODS

9.1 STUDY DESIGN

The study will use observational data from three different countries: the UK, Sweden and Spain. The linaclotide PASS will be a retrospective case-control study nested in a cohort of patients with IBS-C. Cases will be patients suffering from SCD. If the validation is satisfactory (please refer to Section 9.3.4 *Validation of the Diagnosis and Safety Endpoints* below), then both study design components, the case-control and the cohort, will be analysed (please refer to Section 9.7 *Data Analysis* below).

9.2 SETTING

9.2.1 STUDY POPULATION

The source population for the safety study will be:

- UK: patients registered with a GP practice which contributes data to CPRD GOLD or Aurum
- Sweden: patients registered in the NPR linked to the PDR
- Spain: patients registered with a PCP office participating in the SIDIAP

Specific codes for IBS-C and a combination of IBS and constipation codes will be used to identify patients with IBS-C; these are described in [Annex 3](#).

9.2.1.1 INCLUSION/EXCLUSION CRITERIA IN THE IBS-C COHORT

Patients in the study will be required to meet the following inclusion criteria:

- Patient meets IBS-C criteria, as identified through the combination of IBS and constipation codes, (please refer to Section 9.3.4 *Validation of the Diagnosis and Safety Endpoints* below and Annex 3) anytime during the study period
- Patient has at least 12 months of computerised records prior to IBS-C cohort entry date
- Patient meets 'acceptable' criteria from CPRD (the patient is permanently registered at the practice or the PCP and has a valid year of birth and gender) at IBS-C cohort entry date (UK); no equivalent criteria for Spain or Sweden.
- Patient is active (i.e., alive and permanently registered at a practice (UK) or a PCP office (Spain) or the national register (Sweden)) at IBS-C cohort entry date

The following exclusion criteria will apply:

- Patient has no follow-up time (for example, transfers out or dies on the date IBS-C criteria are first fulfilled)
- The practice's up-to-standard (UTS) date in CPRD GOLD is later than the IBS-C cohort entry date (UK); no equivalent criteria for CPRD Aurum, Spain or Sweden*.

*Note: For CPRD GOLD, practices meeting pre-defined quality control standards for completeness, continuity, and plausibility are registered as UTS since the date those standards are met. 'Acceptable' and 'up to standard' are two quality flags that will be taken into account when selecting the study cohort in CPRD GOLD in the UK. In CPRD Aurum, there is no equivalent flag for UTS, therefore, only the 'acceptable' flag will be used for cohort selection. In Spain, no such flags exist but the SIDIAP confirmed that given the study will be performed using data from 2014 onwards, all the data included is of good quality for research purposes. In Sweden, the data received has already been through a quality control by the National Board of Health and Welfare. This control includes checking that compulsory variables like personal registration number, hospital, and main diagnosis are reported, and the validity of all variables values tested. Therefore, no additional changes in the inclusion and exclusion criteria will be needed for Spain and Sweden.

Patients meeting IBS-C inclusion criteria (and not meeting exclusion criteria) at the beginning of the study period (see below) will be prevalent IBS-C patients. Patients meeting IBS-C inclusion criteria thereafter will be incident IBS-C patients.

Inclusion/exclusion criteria for Spain and Sweden will be the same but adapted to the respective database specifics.

9.2.1.2 CASE DEFINITION

Among patients with IBS-C, SCD cases will be patients suffering from diarrhoea (as documented by diagnostic codes) and subsequently (between the diarrhoea diagnosis date and 45 days afterwards) any of the following outcomes:

- Dehydration that requires intravenous rehydration
- Dehydration that requires oral rehydration with solutions of electrolytes
- Electrolyte imbalance: potassium (serum potassium levels 3.0–3.5 mEq/L or < 3.0 mEq/L) and sodium (serum sodium levels > 150 mEq/L)
- Oliguria (urine output < 400 mL in 24 h)
- Anuria (urine output < 50 mL in 24 h)

-
- New-onset thromboembolism episodes
 - New-onset orthostatic hypotension
 - New-onset syncope
 - New-onset dizziness
 - New-onset vertigo
 - Acute renal failure
 - Hypovolemic shock
 - Hospitalisation due to diarrhoea
 - Stupor
 - Coma
 - Death (death certificates will be requested to confirm the cause of death)

The case index date is the date of the first diarrhoea episode that is followed by the first recording of any of the previous outcomes from the list above.

Results of laboratory tests will be available as recorded into only two of the proposed data sources: in CPRD they are manually recorded, especially when they are abnormal; they are automatically recorded in the SIDIAP but there is no lab data information from the Swedish NPR.

9.2.1.3 CONTROL SELECTION

Among patients with IBS-C, each case will be matched by age (initially ± 3 years), the number of years of active history in the database (initially ± 3 years) (CPRD, Swedish NPR or SIDIAP), IBS-C prevalent or incident status, and geographic region and linkage availability (for CPRD only) at index date. Cases will be matched to up to four controls, depending on the number of cases and the total number of cases and controls for validation (see Section 9.3.4 *Validation of the Diagnosis and Safety Endpoints*). Controls will be selected randomly among those patients with IBS-C in the risk set at the case's index date. Cases and controls in the UK will have some variables from their automated information that will be validated through a questionnaire to their attending GPs (see Section 9.3.4 *Validation of the Diagnosis and Safety Endpoints*). Likewise, in Spain case validation will use any additional information obtained through review of free text from medical records by IDIAP's clinical researchers.

Control index date will be set as the same index date of the matched case. An IBS-C patient could, in theory, be a matched control to more than one case. Additionally, a control could, in theory, become a case during its follow-up period.

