4.7 DATA SOURCES

The feasibility of conducting the utilisation and safety study has been assessed in the countries of interest, and the most suitable databases identified are as follows:

- In the UK, the Clinical Practice Research Datalink (CPRD) contains information recorded by GPs as part of their routine clinical practice. Currently, CPRD offers two databases – CPRD GOLD and CPRD Aurum. CPRD Aurum contains data contributed by practices using Egton Medical Information System (EMIS), while CPRD GOLD holds data from In Practice Systems Limited Vision. As of March 2024, CPRD Aurum covered more than 24% of the UK population and CPRD GOLD covered approximately 4.4% of the UK population. Core data in both databases include information on socio-demographic characteristics, diagnoses, symptoms, referrals, tests ordered, some test results, prescriptions issued, and additional clinical information. Prescriptions as prescribed by the primary care physician (PCP) or GP have fields for strength and dose. Medical data in CPRD Aurum are coded using a mixture of Read, Systematized Nomenclature of Medicine Clinical Terms (SNOMED), and local EMIS codes; medical data in CPRD GOLD are coded using the Read coding system only. When linked to secondary care data from the Hospital Episode Statistics (HES), hospitalisation reasons for admission are coded by the International Statistical Classification of Diseases and Related Health Problems, 10th revision (ICD-10); hospital tests and hospital procedures are coded by operating procedure code supplement (OPCS) codes.

There is a potential for overlap between the two CPRD databases, since several GP practices that previously contributed data to CPRD GOLD when using In Practice Systems Limited Vision software are now supported by EMIS software, and have agreed to contribute data to CPRD Aurum. Where this is the case, duplicates will be removed, and only data from CPRD Aurum will be retained.

GPs can be contacted by researchers to request details beyond what can be found in the computerised records or to confirm details of patient conditions and treatments. The latest version of the datasets as of the data application date will be used.

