Initially, we proposed conducting the study with data collected up to December 2016, but based on the patients counts accrued by December 2016, the data collection period was extended. In the current version of the protocol, the data collection period has been extended to the date of the most recent data available in HES and CPRD at the time of data access for the UK only. As CPRD including Aurum data is about two times larger than the last data extraction, we expect more than 200,000 patients with IBS-C in CPRD. Among them, based on market uptake forecasts, we would also expect having around 2,000 patients exposed to linaclotide by that date (as potential risk factor of interest, or approximately 1% of patients with IBS-C).

If SCD occurs with a frequency of 0.05% among patients with IBS-C (cases) and we select one or more controls per case, then 94 case-controls sets would allow the detection of OR = 4 (or larger), with 80% power for a risk factor present in 5% of controls (approximately the expected proportion of patients with IBS-C exposed to linaclotide).

If we assume that SCD occurs with a frequency of 0.08%, then around 168 case-control sets would allow the detection of OR = 3 or larger, with 80% power for a risk factor present in 5% of controls (in bold in Table 3).

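### UK control sampling treats CPRD GOLD and CPRD Aurum as one source although their code lists and quality filters differ; source database should be a matching or adjustment factor

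*Protocol*

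**What the plan says.** The UK source population in Section 9.2.1 joins the two databases: "UK: patients registered with a GP practice which contributes data to CPRD GOLD or Aurum". Section 9.2.1.3 lists the matching factors as age, "the number of years of active history in the database (initially ± 3 years) (CPRD, Swedish NPR or SIDIAP"), and then "IBS-C prevalent or incident status, and geographic region and linkage availability (for CPRD only) at index date". CPRD is named there as a single database. The draw itself is unrestricted: "Controls will be selected randomly among those patients with IBS-C in the risk set at the case's index date". Source database is also absent from the confounder list (Section 9.3.2) and from the Cox and conditional logistic models (Sections 9.7.2.2 and 9.7.3.1). Heterogeneity is tested between countries (Section 9.7).

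The protocol itself describes the databases as different. Section 4.7 says that Aurum mixes Read, SNOMED and local codes, whereas "medical data in CPRD GOLD are coded using the Read coding system only". Section 9.2.1.1 applies the up-to-standard date to GOLD alone, because "In CPRD Aurum, there is no equivalent flag for UTS". Annex 3 gives GOLD and Aurum separate lists for the cohort, for diarrhoea and for SCD.

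**The concern.** A matched comparison assumes that case and control would have been recognised as cases by the same rule. Here the rule depends on the database, and the sampling does not hold database fixed. If recorded SCD is more frequent in one database and linaclotide use also differs between them, part of the UK odds ratio reflects which database supplied the cases. An error downward could hide harm in a safety study; an error upward could suggest harm that is not there. If the cohort analysis is triggered, a UK Cox model without a database stratum would be open to the same problem.

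**Working it through.** **Do the lists differ in substance?** Setting the Annex 3 tables side by side:

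- IBS with diarrhoea is marked as an exclusion code in the Read list (Table 4). It stands in the Aurum IBS-1 list (Table 7), where any code qualifies a patient as having IBS.
- GOLD requires one preferred constipation code. Aurum accepts any code in Table 10, including overflow diarrhoea.
- The Aurum diarrhoea list (Table 13) includes a code recording that diarrhoea was absent. The Read list (Table 11) has no such code.
- The Aurum SCD list (Table 16) names deep vein thrombosis and pulmonary embolism. The Read list (Table 14) has neither. Some differences run the other way: Table 14 has glomerulonephritis codes, flagged as not specific.

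**The plan's own sample size.** Section 4.8 gives 401 pairs for an odds ratio of 4 and 745 for 3, with 1% of controls exposed. With P = OR/(1+OR), p0 = 0.01 and p1 = p0·OR/(1+p0(OR−1)), pairs = [1.96/2 + 0.8416·√(P(1−P))]² / (P−0.5)² / [p0(1−p1)+p1(1−p0)].

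- OR 4: 19.26/0.04806 = 400.8, so 401.
- OR 3: 28.92/0.03882 = 744.9, so 745.

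Both agree. Database does not enter the formula, so matching on it leaves these counts unchanged at the same control exposure.

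**Possible bias.** Inputs:

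- GOLD share g. Section 4.7: "CPRD Aurum covered more than 24% of the UK population and CPRD GOLD covered approximately 4.4% of the UK population". So g = 4.4/(24+4.4) = 0.155. A 50:50 split is an assumed other end, prompted by Section 9.5.2: "As CPRD including Aurum data is about two times larger than the last data extraction".
- Exposure pA (Aurum) and pG (GOLD): assumed between 1% and 4%. Section 4.8 gives that range across the three countries, not by CPRD database.
- Ratio r of recorded SCD rates, Aurum to GOLD: assumed 0.5 to 3. No figure is given.

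With no true effect and controls drawn without regard to database:

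- exposure in cases pc = [(1−g)·r·pA + g·pG] / [(1−g)·r + g]
- exposure in controls p0 = (1−g)·pA + g·pG
- apparent OR = pc(1−p0) / [(1−pc)p0]

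Example: g = 0.155, pA = 1%, pG = 4%, r = 3. Then pc = (0.02535+0.00620)/2.690 = 1.17%, p0 = 0.00845+0.00620 = 1.46%, and the apparent OR is 0.80.

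| Exposure Aurum / GOLD (g = 0.155) | r = 0.5 | r = 1 | r = 2 | r = 3 |
|---|---|---|---|---|
| 1% / 1% | 1.00 | 1.00 | 1.00 | 1.00 |
| 1% / 2% | 1.10 | 1.00 | 0.94 | 0.91 |
| 2% / 1% | 0.94 | 1.00 | 1.04 | 1.05 |
| 1% / 4% | 1.24 | 1.00 | 0.85 | 0.80 |
| 4% / 1% | 0.90 | 1.00 | 1.06 | 1.09 |

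The range is 0.80 to 1.24. At 50:50 it is 0.69 to 1.31. A true odds ratio of 3 would read 2.39 to 3.71 at the stated coverage, and 2.08 to 3.93 at 50:50. The first row and the r = 1 column show that the bias vanishes when either quantity is equal.

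**How many comparisons could be mixed?** With equal case rates and database-blind sampling, 2 × 0.155 × 0.845 = 26% of case-control pairings. Region and linkage matching would lower this by an amount the protocol does not let one compute.

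**The case against.** A reader might infer that database differences do confound the UK odds ratio, or that any difference in linaclotide use between GOLD and Aurum will appear as a drug effect. The protocol supports neither. A difference in exposure alone produces no bias. Ascertainment must differ as well, and both differences must persist within strata of age, history, prevalent or incident status, region and linkage. No exposure or SCD rate is given by database.

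There are real safeguards. Risk-set sampling aligns calendar time. Duplicate records are removed, keeping Aurum. UK cases and controls go to the same GP questionnaire whichever database they come from, which acts on false cases. Validation cannot, however, recover events that a narrower list never flagged, and Section 4.10 reports a very low response in the earlier round. The amendment log (version 13.1) shows that control selection was revised with GOLD and Aurum in mind. Region and linkage in the current text may separate the databases in part, but they remain proxies.

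The size can also be challenged. Section 9.5.2 expects about 1% exposure in CPRD, and the study is sized for odds ratios of 3 or 4. At low exposure, though, the bias depends mainly on the ratio of the two exposures, so a low level does not remove it. The four-fold contrast is an assumption at the extreme.

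Finally, adjustment by database could sit in the statistical analysis plan, which is not at hand, so its absence from the modelling sections is not itself a fault. The matching factors, however, are fixed in the protocol.

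**Conclusion.** The concern holds in conditional form. As written, Section 9.2.1.3 permits matched sets that mix subjects identified by materially different algorithms, and this can bias the UK odds ratio. Neither the presence nor the direction of bias can be established from the protocol. On the assumed inputs, a true odds ratio of 1 could read about 0.80 to 1.24 at the stated coverage. These are upper-end values because region and linkage matching are left out. The Cox model is affected only if the validation thresholds are met and the cohort analysis goes ahead. This is an inexpensive improvement to the design, not a flaw that invalidates the study.

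**What to change.** For UK control sampling still to be done, add source database (GOLD or Aurum) as an exact matching factor in Section 9.2.1.3. For sets already drawn, include a database term in the UK conditional logistic model, run a sensitivity analysis restricted to within-database sets, and report GOLD and Aurum odds ratios separately before combining them. If the cohort analysis is triggered, stratify the UK Cox model and UK incidence by database.

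Full re-matching is not proposed. Section 9.2.1.4 says that potential UK cases had been identified and validation activities initiated by Q2 2024, so re-drawing controls could discard subjects already sent for validation. The remaining costs are modest. Some GOLD cases may have fewer than four controls. The restricted analysis loses the mixed comparisons (up to the 26% above under equal case rates and the stated coverage, fewer if region and linkage already separate the databases), but the model with a database term keeps them. Separate GOLD estimates will be imprecise.

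None of this makes the lists equivalent. Matching or adjusting on database removes the between-database comparison but leaves the Annex 3 discrepancies in place, and these need reconciling separately.
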